1.1 Study Disease

Testosterone is an anabolic steroid and the primary male sex hormone promoting development of male reproductive tissues such as prostate and testis. It can activate androgen receptors in its unchanged form or it can be converted to 5 α -dihydrotestosterone (DHT) by the enzyme 5 α reductase before binding to the androgen receptor. Once bound, the receptor-hormone complex moves into the cell nucleus altering specific gene sequences on the cellular DNA and modifying its transcription, therefore promoting protein synthesis and thus growth of tissues that are sensible to its action.¹ Spermatogenesis is a process that relies on testosterone levels in order to produce good quality sperm cells. This process starts with a primitive germ cell known as spermatogonia; which divides to produce spermatocytes that ultimately form young sperm cells known as spermatids. These last cells then mature and are transformed into spermatozoa or sperm cells. Is in this maturation process where testosterone is crucial. Normal sperm count for a healthy male is higher than 20 million per milliliter.²

Hypogonadism, or low testosterone (Low T), is the deficiency in producing testosterone by the testes. Low T affects more than 10% of men worldwide, with high incidence in the elderly (Haring, et al., 2010). It occurs in association with aging, chronic disease, or other modifiable risk factors such as obesity and diabetes.¹ Testosterone deficiencies have been shown to associated with less muscle mass³, lower bone mineral density⁴, lower hematocrit and hemoglobin concentrations⁵, smaller prostate glands⁶, and diminished energy and sexual function than normal men.^{7,8}

1.2 Study Interventions

Testosterone replacement therapy (TRT) is becoming more widely available and has seen a greater than three-fold increase in use men 40 years and older.⁹ Current delivery systems of TRT include transdermal gels and patches¹⁰, injection therapy¹¹, and long acting subcutaneous pellets.¹² TRT has been shown to improve bone mineral density, prostate volume, energy, and sexual function.⁸ Natesto TM is a relatively new form of TRT that is delivered intranasal to men diagnosed with low T and that has the potential to avoid side effects related to TRT that are commonly seen with other delivery methods. A recent study showed that this medication was well tolerated with very low adverse events and discontinuation rates among patients. ¹¹

1.3 Study Rationale

Current advantages to Natesto TM include ease of delivery and decreased risk of the medication being transfer upon skin contact to woman or children.¹¹ Recently Natesto 4.5% NTG (125 uL/nostril, 11.0mg testosterone/dose) TID dosing was shown to also increase serum testosterone while maintaining normal, though decreased, serum levels of LH and FSH.¹⁶ This has the

theoretical benefit of maintaining normal semen parameters while on TRT with Natesto- to date, this theoretical benefit has not been evaluated.

While Natesto has been shown to have positive effects on Testosterone while maintaining LH and FSH, the impact on sperm count has not yet been proven. Past research has shown a marked reduction in spermatogenesis in topical testosterone gel treatment.¹⁷ Natesto™ has the potential to maintain normal spermatogenesis levels via maintenance of FSH and LH levels in the normal range. Our hypothesis is that Natesto™ will significantly increase Testosterone while having no significant impact on FSH, LH, and serum parameters in men with Low testosterone. A proposed mechanism for this is that the TID dosing of Natesto will maintain pulsatile release of GnRH, preventing marked decreases in serum FSH and LH.

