2. HYPOTHESIS

2.1 Alternate hypothesis

Natesto™ will not change sperm count by $\pm 10\%$ from baseline.

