3. OBJECTIVES

3.1 Primary Efficacy Objective

Primary outcomes will be changes in LH, FSH, testosterone, estrogen, and quality of life from baseline, 14 weeks ± 7 days and 26 weeks ± 7 days.

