10. STATISTICAL CONSIDERATIONS

10.1 Primary Study Endpoints

The primary endpoint will be change in FSH, LH, Testosterone, and Semen Analysis after 6 months of treatment of Natesto.

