10.4 Statistical Analysis and Power calculation

The average and standard deviation of all relevant variables and baseline characteristics, primary and secondary outcomes will be calculated.

Change in sperm count will be analyzed using the ANOVA and MANOVA. A change in $< \pm 10\%$ will be reject the null hypothesis.

LH, FSH, E and Testosterone levels will be analyzed using one-sample t-test with repeated measures throughout the study.

IIEF-EF and SF-36 questionnaires will be analyzed and compared between the groups according to Fisher's exact test in each of the endpoints. The statistical significance will be set at $P < 0.05$.

Demographic characteristics such as age and testosterone level will be compared between groups A and B using student's test. Other demographic characteristics, such as medical background and risk factors will be compared between these groups using Fisher's exact test.

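### Section 1.3 hypothesises no significant impact on LH and FSH, but section 10.4 tests them only for a difference and gives no margin, confidence-interval rule or normal-range criterion

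*Combined protocol and SAP*

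**What the plan says.** Protocol section 1.3 states, as its hypothesis, that testosterone will rise significantly "while having no significant impact on FSH, LH, and serum parameters in men with Low testosterone". The same section says that Natesto may preserve spermatogenesis "via maintenance of FSH and LH levels in the normal range", and it reports that earlier three-times-daily use lowered LH and FSH but left them normal.

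Both places that name primary outcomes include these hormones. Section 3.1: "Primary outcomes will be changes in LH, FSH, testosterone, estrogen, and quality of life from baseline", with weeks 14 and 26 listed. Section 10.1: "The primary endpoint will be change in FSH, LH, Testosterone, and Semen Analysis after 6 months of treatment of Natesto".

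The analysis is in section 10.4: "LH, FSH, E and Testosterone levels will be analyzed using one-sample t-test with repeated measures throughout the study". Significance is set at P<0.05, with no statement of one or two sides. The descriptive plan is: "The average and standard deviation of all relevant variables and baseline characteristics, primary and secondary outcomes will be calculated".

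The only bound in the plan is the ±10% for sperm count in 2.1, 2.2 and 10.4; the formal alternative hypothesis is that Natesto "will not change sperm count by" that amount. Nothing comparable is given for LH or FSH.

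**The concern.** One test serves two opposite aims. For testosterone the authors hope to show a change, and a t-test of change against zero can show it. For LH and FSH they hope to show little or no change. There the same test can only reject or fail to reject, and failing to reject may simply reflect imprecision.

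This matters because LH and FSH are primary and are the pathway by which 1.3 expects sperm production to be spared. Section 1.3 says of the clinical question itself that "the impact on sperm count has not yet been proven". If the hormone result is reported as preserved because P exceeded 0.05, readers may take the mechanism as shown while the data still allow a real fall.

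The wording of 1.3 adds a second difficulty. It does not say whether significance is meant statistically or clinically. A small fall with P<0.05 that stays within the normal range would count against the hypothesis on the first meaning and agree with it on the second. Section 10.4 does not settle which applies.

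**Working it through.** **The plan's own figure.** Sections 6.3 and 10.3 give 80 men; section 4.1 gives 40. Section 10.4 has power calculation in its title but states no power, effect size, SD, margin or dropout, so neither number can be reproduced. Both are used below; the conflict between them is a separate matter.

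**Assumptions, none from the documents.** Two-sided 5% test; one hormone at one visit; all men evaluable unless stated; approximately normal change scores; true falls of 0.1 to 0.5 SD of the change score.

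**Step 1: chance that a real fall is non-significant.** With true fall d in SD units and n men, the t statistic is noncentral t with n−1 degrees of freedom and noncentrality d√n. The chance of P>0.05 is the probability that it lies within ±t(0.975, n−1).

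- n=40, d=0.3: noncentrality 0.3×√40 = 1.90, critical value 2.023, chance 0.543.
- n=80, d=0.3: noncentrality 0.3×√80 = 2.68, critical value 1.990, chance 0.245 (0.2449 before rounding, so 24%).

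| True fall (SD) | n=40 | n=80 |
|---|---|---|
| 0.1 | 0.905 | 0.857 |
| 0.2 | 0.765 | 0.576 |
| 0.3 | 0.543 | 0.245 |
| 0.4 | 0.306 | 0.058 |
| 0.5 | 0.131 | 0.007 |

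If an assumed 20% of men have no week-26 sample (32 or 64 left), the 0.3 SD row becomes 0.624 and 0.343.

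**Step 2: what the interval can exclude.** The 95% CI half-width is t(0.975, n−1)/√n in SD units.

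- n=40: 2.023/√40 = 0.320.
- n=80: 1.990/√80 = 0.223.

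With an observed mean change of exactly zero, falls up to 0.32 or 0.22 SD remain compatible with the data. At the extreme, an observed fall just short of significance is itself about one half-width, so the lower limit is twice that: 0.64 or 0.45 SD.

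**Step 3: what 10.4 offers besides the test.** Means and SDs. If the SD of the change is among them, a reader can compute the interval from mean, SD and n. No section says how that interval would be judged.

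**The case against.** A reader might infer that the plan will declare LH and FSH preserved whenever P>0.05, or that a non-significant test is the only support it could ever produce. The documents do not support either inference. No section states such a decision rule, the formal hypotheses in section 2 concern sperm count alone, and 3.1 and 10.1 define the LH and FSH endpoints neutrally as change. Section 10.4 also plans means and SDs, from which an interval may be derived.

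A reader might also infer that any small significant fall would refute the hypothesis. Section 1.3 does not force that. It describes earlier results as lower but still normal, relies on the normal range, and proposes a mechanism that prevents marked decreases. Together these permit a clinical reading. Against that, the same sentence uses the word significantly for the testosterone rise, which favours the statistical reading.

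The magnitudes have no anchor in the documents. They are in assumed SD units, so their clinical size is unknown. The 0.64 and 0.45 SD figures are boundary cases in which the observed fall would be visible in the reported mean. With 80 men, a 0.5 SD fall would almost never be missed (0.7%).

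What stands is that, on either reading, 10.4 contains no criterion. The statistical reading needs a bound on the change, the clinical reading needs a range or a limit, and the plan carries neither into the analysis. The choice of visit and the meaning of repeated measures in 10.4 are separate questions and add nothing to this one.

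**Conclusion.** The concern holds in limited form. The only inferential analysis planned for LH and FSH cannot by itself support the hypothesis stated for them, and nothing in the plan says how the accompanying means and SDs would be judged. It should be fixed, because it governs how primary results are read, but it is a gap in interpretation and not a stated wrong rule.

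For moderate falls the test's silence is weak evidence: at an assumed 0.3 SD it misses the fall about half the time with 40 men and about a quarter of the time with 80. These rates depend on the assumed effect, full follow-up and a two-sided test. The logical point does not depend on them.

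**What to change.** In section 10.4:

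1. Report mean change from baseline in LH and FSH with 95% CIs at weeks 14 and 26, with week 26 primary in line with 10.1.
2. State that P>0.05 will not be read as no effect.
3. Label the LH and FSH results as estimation only, unless a margin with a reason and the CI level that judges it are stated in advance.
4. Keep the t-test for the increase in testosterone.

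In section 1.3, reword the hypothesis to match and say which meaning of no significant impact is intended.

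Cost: a narrower claim about LH and FSH, and a little more analysis. No new samples are needed, since the study calendar already has FSH and LH drawn at visits 1, 4 and 6.

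A formal claim of maintenance would cost more, because the sample size would need justifying. As an illustration, take an assumed equivalence margin of ±0.3 SD judged by a 90% CI, with no true change. Power per hormone is then about 18% with 40 men and 69% with 80, and 97 evaluable men are needed for 80%. The estimation-only label avoids that cost.

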2. HYPOTHESIS

2.1 Alternate hypothesis

Natesto™ will not change sperm count by $\pm 10\%$ from baseline.

2.2 Null Hypothesis

Natesto™ will change sperm count by $\pm 10\%$ from baseline.

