7. STUDY DESIGN, CLINICAL, RADIOLOGICAL, LABORATORY AND SURGICAL EVALUATIONS

7.1 Study Design

This is a prospective clinical study aimed to evaluate the safety and efficacy of Natesto TM on patients with idiopathic hypogonadism. Clinical signs and symptoms of hypogonadism, i.e. diminished energy and sexual function; and/or a decreased sperm count constitute the clinical indication for TRT in our study population.

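### The ±10% sperm-count rule makes a mean rise above 10% fail the Section 2 hypothesis just as a fall does, and the plan gives no reason for the upper limit

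*Combined protocol and SAP*

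**What the plan says.** The alternative hypothesis (2.1) is that Natesto "will not change sperm count by $\pm 10\%$ from baseline"; the null (2.2) is that it "will change sperm count by $\pm 10\%$ from baseline". Section 10.4 gives the decision rule: "A change in $< \pm 10\%$ will be reject the null hypothesis". Nothing in the plan treats a rise differently from a fall.

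The purpose is set out in 1.3. The drug has the "theoretical benefit of maintaining normal semen parameters while on TRT with Natesto", and the contrast drawn is with another product: "Past research has shown a marked reduction in spermatogenesis in topical testosterone gel treatment". The proposed route is hormonal: Natesto "has the potential to maintain normal spermatogenesis levels via maintenance of FSH and LH levels in the normal range". On sperm, Section 8.1 (expected adverse events) mentions only a lowered count and occasional azoospermia.

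On the population, 6.1 item 4 admits men with a count below 20 million/mL as one possible entry feature, and 6.2 item 5 excludes those below 1 million. Section 7.1 says that symptoms "and/or a decreased sperm count constitute the clinical indication for TRT in our study population". Section 1.1 puts a normal count above 20 million/mL.

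**The concern.** The question behind the study is whether this form of testosterone avoids the sperm loss seen with gel. A rule that answers it needs a floor. The written rule also has a ceiling, so it gives the same answer to a 15% rise and a 15% fall: the null is retained and the Section 2 hypothesis fails.

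The mismatch is sharpest for men with low counts. A man who goes from 10 to 12 million/mL has changed by +20%. He has moved towards the protocol's own normal value, yet he lies outside the success zone, while an unchanged count of 10 lies inside it. If enough such men enrol and the mean rises, the only hypothesis stated in Section 2 would be reported as not supported, although no sperm were lost.

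**Working it through.** The plan has no figure to reproduce. Section 10.4 has power calculation in its title but gives no SD, expected change or power. The direction of the rule is settled by reading 2.1, 2.2 and 10.4 together; the arithmetic below only shows how much it matters.

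**Inputs**
- Limits: ±10% (2.1, 2.2, 10.4). On the log scale, ln 0.90 = −0.1054 and ln 1.10 = 0.0953.
- Sample size: 40 (4.1) or 80 (6.3, 10.3). The sections conflict, so both are shown.
- Assumed: the rule is applied to the mean log change as a point estimate; SD of individual log change 0.5 (range 0.4 to 0.7); normal approximation.
- Assumed true changes: +15% (ln 1.15 = 0.1398), zero, and −15% (ln 0.85 = −0.1625).

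**Standard error.** SE = SD/√n: 0.5/√40 = 0.0791; 0.5/√80 = 0.0559.

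**Formulas**, with μ the true log change:
- Two limits, as written: Φ((0.0953 − μ)/SE) − Φ((−0.1054 − μ)/SE)
- Lower limit only, still a point estimate: 1 − Φ((−0.1054 − μ)/SE)
- One-sided 95% lower confidence bound above −10%: 1 − Φ((−0.1054 − μ)/SE + 1.645)

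**True change +15%**
- n=40, two limits: Φ(−0.562) − Φ(−3.101) = 0.286. Lower limit only: 1 − Φ(−3.101) = 0.999.
- n=80, two limits: Φ(−0.795) − Φ(−4.385) = 0.213. Lower limit only: above 0.999.

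**True change zero**
- n=40, two limits: Φ(1.206) − Φ(−1.333) = 0.795. Confidence bound: 1 − Φ(0.312) = 0.378.
- n=80, two limits: Φ(1.705) − Φ(−1.885) = 0.926. Confidence bound: 1 − Φ(−0.240) = 0.595.

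Probability that the hypothesis is declared supported, SD 0.5, n=40 / n=80:

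| True change | Point estimate within ±10% | Point estimate above −10% | One-sided 95% bound above −10% |
|---|---|---|---|
| +15% | 29% / 21% | >99% / >99% | 93% / >99% |
| 0 | 79% / 93% | 91% / 97% | 38% / 60% |
| −15% | 23% / 15% | 23% / 15% | 1% / <1% |

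The second and third columns differ only in direction, so they are the like-for-like comparison. Dropping the upper limit changes the verdict on a rise and leaves the verdict on a 15% loss as it was. The last column also changes the standard of evidence, which is a separate decision.

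**Sensitivity.** At +15%, over SD 0.4 to 0.7 and both sample sizes, the two-limit rule is met in 16–33% of trials and the lower-limit point-estimate rule in 99–100%. On a percent scale with an assumed SD of 50 points and n=80, the two-limit rule is met with probability 0.04 at a true +20% and also 0.04 at −20%; with the lower limit only, these become 1.00 and 0.04.

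**The case against.** **Equivalence may be intended.** To maintain a count can mean to keep it unchanged, and 1.3 does hypothesise no significant impact, although that sentence names FSH, LH and serum parameters, not sperm count. A reader might infer that every statement in the plan runs in one direction; that is too strong. No section says outright that a rise is favourable: this is inferred from 1.1 and 7.1. What survives is that the argument given for sperm concerns avoiding suppression, and that nothing justifies an upper limit.

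**Low-count men are permitted, not required.** Item 4 of 6.1 uses an and/or condition, so their share is unknown. This limits how likely a large rise is. It does not alter how the rule treats one.

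**An upper limit has some use.** In a before-after design, men admitted with low counts may drift upward on retest, and under a lower-limit rule such drift could mask a real loss. This stands, and is why the fix includes the choice of baseline.

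**The weight of the criterion is unclear.** Sperm count is secondary in 3.2, semen analysis is part of the primary endpoint in 10.1, and semen parameters are exploratory in 10.2. It is nevertheless the only hypothesis stated in Section 2.

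**A failed result need not hide its direction.** A reader might infer that the trial could not tell harm from improvement. The documents do not support that: 10.4 provides for means and standard deviations of the primary and secondary outcomes, so a rise would be visible.

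**Conclusion.** The point holds as a mismatch between the decision rule and the question. Under 2.1, 2.2 and 10.4, a mean rise above 10% is a failure of the Section 2 hypothesis, and the plan offers no reason why it should be. What is wrong is the conclusion attached to a rise; information about it is not lost.

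At an assumed true rise of 15% and log-scale SD of 0.5, the ceiling alone cuts the chance of success from over 99% to 29% (n=40) or 21% (n=80). The SD, the size of the rise and the point-estimate reading of 10.4 are all assumptions; the symmetry of the rule is not.

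A reader might also set 29% or 21% against the confidence-bound results of 93% and over 99% and credit the whole gain to direction. That comparison changes the direction and the standard of evidence together, and it conceals that the bound makes success at zero true change less likely than the rule as written.

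**What to change.** Restate 2.1, 2.2 and the rule in 10.4 so that only the lower limit decides, keeping the existing 10%. Null: sperm count falls by 10% or more. Alternative: any fall is less than 10%. Report rises descriptively, without claiming a drug benefit, since the plan describes no control arm (10.4 mentions groups A and B but no section defines them).

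Use the Visit 2 semen sample in the study calendar (Section 12) as baseline, or include it in the baseline, to limit regression to the mean after selection at screening. Visit 2 is also the first dispensing visit, so the plan should state that the sample precedes the first dose.

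If two-sided equivalence is truly intended, keep the upper limit and justify it.

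**Cost.** The change is one of wording and needs no new data, since the Visit 2 sample is already scheduled. The claim narrows from no change to no loss of 10% or more. Whether the limit applies to the point estimate or to a one-sided 95% confidence bound is a separate matter and should be stated. If the bound is chosen, disclose that at zero true change and SD 0.5 success falls to about 38% (n=40) or 60% (n=80), from 79% or 93% under the point-estimate rule as written. That is a sample-size consequence, which 10.3 and 10.4 would then have to address.

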3. OBJECTIVES

3.1 Primary Efficacy Objective

Primary outcomes will be changes in LH, FSH, testosterone, estrogen, and quality of life from baseline, 14 weeks ± 7 days and 26 weeks ± 7 days.

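### Sections 3.1 and 10.1 name different primary outcomes and times, and 10.4 gives only P < 0.05, so the error rate for primary claims of change is uncontrolled (about 13–40%, depending on the set)

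*Combined protocol and SAP*

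**What the plan says.** Three sections bear on the primary analysis.

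- **Section 3.1:** "Primary outcomes will be changes in LH, FSH, testosterone, estrogen, and quality of life from baseline", at "14 weeks ± 7 days and 26 weeks ± 7 days". That is five outcomes at two visits, with neither visit ranked above the other.
- **Section 10.1:** "The primary endpoint will be change in FSH, LH, Testosterone, and Semen Analysis after 6 months of treatment of Natesto". That is four outcomes at one time. Estrogen and quality of life are absent, and semen analysis is added.
- **Section 10.4:** "LH, FSH, E and Testosterone levels will be analyzed using one-sample t-test with repeated measures throughout the study". The two questionnaires, IIEF-EF and SF-36, are to be tested at each endpoint. Then: "The statistical significance will be set at" P < 0.05. There is no adjustment, no order of testing, and no statement of whether one or all primary outcomes must succeed.

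The only decision rule in 10.4 is the ±10% rule for sperm count. Section 3.2 calls sperm count secondary, 10.1 puts semen analysis in the primary set, and 10.2 labels the semen parameters exploratory. Section 1.3 expects testosterone to rise and FSH and LH not to be significantly affected.

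**The concern.** With two primary definitions and one blanket threshold, the plan does not fix which result carries the primary claim. An analyst could follow 3.1 and report whichever of its outcomes and visits crosses 0.05, or follow 10.1 and use a different list at one time. Either would be consistent with the text. A result reported as a significant primary change would then carry a nominal 5% error that the plan does not deliver.

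The outcomes also point in different directions. Testosterone is meant to change, while LH and FSH are meant not to. A single significance threshold cannot serve both aims.

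**Working it through.** **The plan's own figure.** The only error rate stated is P < 0.05 per test. It is declared rather than derived, and no family-wise rate is given, so there is nothing to reproduce.

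**Inputs**

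- Level per test: 0.05 (10.4). Sidedness is not stated; two-sided is assumed.
- 3.1 set: 5 outcomes × 2 visits = 10 tests, with quality of life counted once.
- 10.1 set: 4 outcomes × 1 time = 4 tests, with semen analysis counted once.
- Questionnaires: 2 instruments at each of Weeks 14 and 26 (7.4).
- Correlations: none are given, so a range is assumed.

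**Formula.** For m independent tests with all nulls true, the chance of at least one false significant result is 1 − 0.95^m:

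- m = 4: 1 − 0.8145 = 18.5%
- m = 6: 1 − 0.7351 = 26.5%
- m = 8: 1 − 0.6634 = 33.7%
- m = 10: 1 − 0.5987 = 40.1%

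**Allowing for correlation.** Multivariate-normal test statistics were simulated (200,000 draws, two-sided 0.05). For the 10- and 8-test sets, the correlation was 0 to 0.7 between outcomes and 0.5 to 0.9 between visits of the same outcome. It was the product of the two where both differ. For the 4- and 6-test sets, one common correlation of up to 0.7 was used.

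| Set | Tests | Independent | Correlated (assumed) |
|---|---|---|---|
| 10.1: four outcomes, 6 months | 4 | 18.5% | about 16% at 0.5; 13.0% at 0.7 |
| 3.1: five outcomes, two visits | 10 | 40.1% | 37.9% (0 and 0.5) down to 20.0% (0.7 and 0.9) |
| 3.1 without testosterone | 8 | 33.7% | 31.5% down to 17.8% |
| Estrogen and one quality-of-life result, two visits | 4 | 18.5% | 13.0% at 0.7 |
| Estrogen, IIEF-EF and one SF-36 score, two visits | 6 | 26.5% | 20.9% at 0.5; 16.3% at 0.7 |

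The last two rows drop testosterone because its null is expected to be false. They drop LH and FSH because a chance significant change there would count against the study's hypothesis, not for it.

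**Which visit is 6 months?** The study calendar first dispenses drug at Week 2, and 26 − 2 = 24 weeks. That matches the treatment course in 4.2, so Week 26 is the visit that 10.1 describes.

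**The case against.** The strongest reply has four parts.

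1. **10.1 does name a time.** This stands. A reader might infer that the plan has no primary time at all, but 10.1 says "after 6 months of treatment of Natesto". The fault is that 3.1 contradicts it.
2. **The number of tests is uncertain.** A reader might count 15: LH, FSH and estrogen at two visits (6), testosterone at five (5), and two questionnaires at two (4). Independent tests would then give 1 − 0.95^15 = 53.7%. The documents do not support this as a primary family. Weeks 6, 15 and 27 are primary times in neither section, and 3.1 lists quality of life as one outcome. The hormone sentence in 10.4 could even mean one repeated-measures analysis per hormone. Five tests, one per outcome, would give 22.6% if independent and about 15% at correlation 0.7.
3. **Not every false positive is a false success.** This also stands. Section 1.3 expects testosterone to rise and hopes for no effect on LH and FSH, and 2.1 hopes for no change in sperm count. If 10.1 alone governed, its 13–18.5% would be a rate of false findings of change and not of false success. For LH and FSH the greater weakness is reading a non-significant test as no effect.
4. **The threshold and the questionnaire tests are loosely specified.** The P < 0.05 sentence sits in the questionnaire paragraph, so applying it to hormones is an inference, though it is the only level given. Fisher's exact test is to compare groups that the design never defines, so it cannot be run as written. It also tends to reject below its nominal level, which would lower the questionnaires' share.

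None of this supplies a success rule or reconciles the two sections.

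**Conclusion.** The concern holds as a conflict between two primary definitions with no multiplicity or success rule. If the nulls tested are true, the chance of at least one false significant change is about 13–18.5% under 10.1 and about 20–40% under 3.1.

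A reader might take 20–40% as the chance of a false success. The documents do not support that, because the figure includes testosterone, LH and FSH. On estrogen and quality of life alone the figure is about 13–18.5% (four tests) or 16–26% (six tests).

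These figures rest on two-sided tests at 0.05, on 10.4's threshold applying to every outcome, on quality of life and semen analysis being counted as stated above, and on assumed correlations. If the two visits of one outcome correlate above 0.7, the lower ends of the four- and six-test ranges fall somewhat further. The need for a rule does not depend on the exact figure.

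**What to change.** Edit 3.1, 10.1 and 10.4 together, so that no section is left contradicting another.

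1. Name one primary set, with Week 26 as the only primary time.
2. Test the testosterone rise at Week 26 first, at two-sided 0.05.
3. Make estrogen, the questionnaire scores and testosterone at other visits secondary, with Holm adjustment for claims of change. Name the SF-36 score to be used, and define a questionnaire comparison that this design can run.
4. Report LH and FSH at Weeks 14 and 26 as estimates with 95% confidence intervals. Do not apply a multiplicity correction to their change tests, since a stricter threshold would make a claim of no impact easier. Do not read a non-significant result as no impact. Any claim of preservation needs a margin, which the documents do not give and the sponsor must set in advance.
5. State the rank of the sperm result consistently in 3.2, 10.1 and 10.2.

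**Cost.** No patients or visits are added, but a margin must be chosen if preservation is to be claimed. Some secondary changes will no longer be called significant. The secondary family would be 6 tests (estrogen and two questionnaire scores at two visits) plus 4 (testosterone at Weeks 6, 14, 15 and 27), so Holm's strictest step is 0.05 / 10 = 0.005. The standardised change detectable with 80% power is (z for the level + 0.84) / √n. At that step it goes from (1.96 + 0.84) / √80 = 0.31 to (2.81 + 0.84) / √80 = 0.41 with 80 men (6.3, 10.3). With 40 men (4.1) it goes from 0.44 to 0.58.
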